## Protocol Summary Form

9. Use of: investigational medication within past 3 months; depot antipsychotic within past 6 months; serotonergic medication within past 2 weeks (6 weeks for fluoxetine). The ADC will not take subjects off medication for the purpose of entering this study.
	
Psychiatric and Medical History

10. Current cognitive-behavioral therapy (CBT) specific for BDD
	
Psychiatric History

11. History of seizure disorder, other than febrile seizure in childhood
	
Medical History

12. Presence of significant or unstable medical illness
	
Medical History, vital signs, EKG, blood and urine tests, physical examination

13. Females who are pregnant, breastfeeding, or sexually active and not willing to use adequate contraception
	
Medical History, urine pregnancy test

14. Presence of any other conditions that would preclude safe administration of psilocybin based on clinical judgement of the PI and/or therapist. This includes but is not limited to any behaviors suggesting the participant will be unable to establish therapeutic alliance with the therapist
	
Psychiatric Assessment

15. Enrollment in any investigational drug or device study in past 30 days
	
Psychiatric History

16. Dissociative Disorder
	
Psychiatric Assessment

Describe whether and how subjects will be provided with additional pertinent information after participation.  
N/A

### Waiver of Documentation of Consent

Would the consent form signature be the only link between the subject's identity and the research data? N/A

Is breach of confidentiality the main study risk? N/A

Is consent for this research procedure ordinarily not required outside of the research context? Explain.  
N/A

Describe the study component(s) for which waiver of documentation is requested. N/A

### Waiver of Parental Consent

Explain why parental/guardian consent is not a reasonable requirement to protect the minor participants in this study. N/A

If parental consent is waived, describe a mechanism that will be substituted to provide appropriate protections for the subjects. N/A

### Assent Procedures

*In this section, please describe the procedures by which subject assent will be assessed and / or recorded.*

N/A

### Independent Assessment of Capacity

*This section is designated for those studies that have been identified where subjects **May Lack** capacity to consent.*

Describe the Methods/procedures for capacity assessment. N/A

If your study involves subjects who **DO LACK** capacity to consent, please justify. N/A

Procedures for surrogate consent. N/A

### Study Procedures

*Provide a clear, concise narrative of study procedures with special attention to the subjects' involvement. Detail the overall study timeline and location of study procedures, list all interventions, assessments and interviews, estimate the duration of each procedure, provide dosing schedules, identify study personnel involved in each procedure, and provide credentials for relevant personnel. If treatment is provided, specify the minimum credentials for providing that treatment. For complicated study designs, we strongly encourage attaching tables, flow-charts, and study algorithms.*

I attest to follow the COVID-19 Safety Guideline for Columbia Psychiatry and NYSPI Re-Entry outlined in the NYSPI Director's June 1, 2020 memo, which include but are not limited to:

- Infection Control/PPE – Guidelines
- Research participants will only come on-site if absolutely necessary for study procedures.
- Clinical research teams will screen their participants for COVID symptoms (night before and day of onsite visit, documenting this in the chart), and escort them in and out of the building.
- COVID/COVID-like symptoms in participants will be reported to the IRB via PRISM as an SAE.

COVID testing: Depending on COVID conditions in the community, the participant and the two therapists scheduled to be with the participant during the psilocybin day may be tested at NY State Psychiatric Institute on the day before psilocybin dosing, to determine if any may currently be infected with the virus that causes COVID-19. The test involves collecting a sample by putting a cotton swab several inches into the nose. If the test shows that the participant or either therapist has COVID-19, your research treatment visit will be postponed.

Internet-based data collection or transmission will be conducted following HIPAA and NYSPI guidelines.

**1. Visit 1 (Screening).** A complete psychiatric and physical examination will be performed, including Psychiatric, Medical and Social Histories, MINI Structured Psychiatric Interview, SCID-5 BDD module, Hamilton Rating Scale for Depression, Columbia Suicide Severity Rating Scale, and standard laboratory testing including EKG, urine for routine analysis, drugs of abuse and (if appropriate) pregnancy and blood for hematologies and

chemistries including thyroid function. A physical examination will be performed at the screening or between screening and Visit 2 (Day -1), with results obtained before psilocybin administration day.

Additional screening will specifically assess eligibility for the MRI portion of the study with the self-rated PhenX Toolkit Hand Dominance Measure and MRI Metal Screening Questionnaire. Contraindications to MRI scanning are:

- Paramagnetic metallic implants or devices
- Contraindicating magnetic resonance imaging or any other non-removable paramagnetic metal in the body (e.g., pacemaker, paramagnetic metallic prosthesis, surgical clips, shrapnel, necessity for constant medicinal patch, some tattoos)
- Being unable to tolerate the scanning procedures (i.e., severe obesity, claustrophobia)

Patients with contraindicated metal or left-handedness will not be offered MRI participation but will complete all other parts of the protocol.

Additional visits (V1a, V1b) will be scheduled as needed to follow up on any lab abnormalities and for patient to establish relationship with study therapist.

Participants will be invited to bring to the screening a companion (friend/family member) whom they would like to support them through the study. Such a companion will be informed of their potential role and will be asked to sign a “caregiver” consent form at the Screening Visit. Caregivers will receive information about the signs of worsening of depression and suicide risk and ways to contact the study team if necessary. The caregiver will complete a questionnaire at screening, Week 3 and Week 12.

**2. Visit 2 (Baseline, Day -1).** Eligibility and willingness to participate will be reassessed. At this visit, the patient meets with the therapist who describes what the experience might be like and how the therapist will handle any difficulties the patient may have with the experience. MRI-eligible subjects will complete acquisition of resting state fMRI. Subjects will also complete an inverted face computer task in which they will view an image of a face and then will be shown an image of two faces (one matching and one non-matching morphed face) and asked to select the matching face as rapidly and accurately as possible. The matching and non-matching faces will be presented either upright or inverted, in various combinations. This task assesses global vs. local visual processing, and it has previously been shown to be abnormal in BDD (Feusner, 2010).

**3. Visit 3 (Psilocybin Day, Day 0).** The next day, a study psychiatrist again assesses eligibility; those eligible and agreeable receive their dose of psilocybin (25 mg) and spend the next eight hours (longer if needed) with the two therapists; when deemed appropriate, the patient is accompanied home either by a person of their choosing or a staff member. The patient will be reminded that they should not drive or drink alcohol at least until after the end of Visit 4 (next day). Vital signs are taken prior to their dose of psilocybin and prior to leaving the clinic and a study psychiatrist evaluates prior to their departure for whether their condition requires them not to leave. In the latter case, they will either remain in the Biological Studies Unit (BSU) until

cleared by a study psychiatrist or admitted to 5-South inpatient service if they require additional observation overnight.

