### Lay Summary of Proposed Research

*This section is intended to provide a basic overview of the study including a description of its purpose, study procedures, and subject population. The summary should provide a concise overview of the study for non-scientific and scientific members of the IRB. Please avoid medical or technical terminology. In general, the abstract of a grant does not provide a suitable lay summary.*

Body dysmorphic disorder is a common condition characterized by symptoms of "imagined ugliness" with debilitating distress, checking and avoidance behaviors, and seeking unnecessary cosmetic medical procedures. Serotonin reuptake inhibitor medications and cognitive behavioral therapy helps some patients, but many do not benefit from existing treatments, and no medications are FDA-approved for this indication. Psilocybin is under development as a treatment of several psychiatric disorders, with placebo-controlled trial evidence of safety and prolonged efficacy for major depression when administered as a single dose with intensive support by a therapist on the day of administration. A single case report in body dysmorphic disorder suggests psilocybin might also have efficacy for this disorder.

In this proposed pilot study, up to 12 adults with body dysmorphic disorder that has not responded to at least one adequate trial of a serotonin reuptake inhibitor will be treated openly with a single oral dose of psilocybin. Procedures will follow those previously established in depression studies of psilocybin. Patients will receive intensive preparation and support from two therapists, including 8-9 hours accompanying the patient on the day of medication administration in the Biological Studies Unit. Follow-up visits to monitor safety and clinical outcome will be conducted at day 1, week 1, and months 1, 2, and 3 post-administration. Resting state MRI will be conducted prior to and one day after psilocybin administration to assess the effect of medication on brain circuits.

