## Risks/Discomforts/Inconveniences

*"Risk" is a broad term used to convey the potential for harm, burden, and inconvenience related to research participation. Use this section to provide a comprehensive description of foreseeable physical, psychological, social, interpersonal, and economic risks introduced by the research. Include the source of the information. Consider both the probability and magnitude of harm and its impact. Describe the foreseeable harms associated with the research (untoward effects of a medication) and those related to delay to individualized treatment. Include data from the literature, and local data, if available, on risk rates and subject experiences with research procedures. Describe procedures in place to minimize risk. In general, please create a numbered list of risks/categories of risk, and in general put the list in the order of significance or level of risk, the most significant risks should be listed first.*

1. BDD might not remit or may worsen
2. Psilocybin has not been extensively studied, so both short and especially long-term consequences of its use may not be known at present
3. Known psychological effects of psilocybin include:
  - a. Euphoric mood
  - b. Dissociative experience (i.e., feeling outside one's body or unreal, a distorted sense of time)
  - c. Hallucinations (**which may persist for weeks after dosing**)
  - d. Psychotic experience such as paranoia
  - e. Difficulty with cognition (e.g., trouble adding or solving puzzles)
  - f. Disturbance in attention
  - g. Mood alteration
  - h. Inappropriate affect (e.g., crying when one is not sad or laughing when nothing odd occurred)
4. Known medical effects of psilocybin include:
  - a. clumsiness
  - b. feeling weak
  - c. headache
  - d. hyperreflexia (e.g., the lower leg reacts too strongly when the knee tendon is tapped)
  - e. hyporeflexia (e.g., the lower leg under-reacts when the knee tendon is tapped)
  - f. increased blood pressure
  - g. increased pupil size
  - h. rapid heart beat
  - i. tremor
  - j. vomiting
5. Discomfort of needle sticks and ECG
6. Time commitment to completing forms, and attending evaluation, treatment and follow-up sessions
7. Harm to an unborn or newborn child

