  - i. Inappropriate affect (e.g., crying when one is not sad or laughing when nothing odd occurred) – this will be monitored by clinical observation and the PANAS and dealt with as part of the therapist's interaction with the patient.
4. Known medical effects of psilocybin:
  - a. Clumsiness - a staff member will remain with patient at all times ready to prevent falls as needed (e.g., traveling to and from the bathroom)
  - b. Feeling weak - ditto
  - c. Headache - standard headache remedies (i.e., NSAID's)

- 
- d. Hyperreflexia - reassurance and waiting
  - e. Hyporeflexia – reassurance and waiting
  - f. Elevated blood pressure - watchful waiting as to date, the blood pressure has not been documented to get to dangerous levels (i.e., systolic pressure may get to 160 mm Hg); as blood pressure rises typically last 1-3 hours, a short-acting blood pressure lowering medication such as nifedipine could be considered
  - g. Increased pupil size - keep in darkened room (this is the standard lighting in psilocybin rooms)
  - h. Rapid heartbeat - watchful waiting as to date, fast heart rate has lasted 1-3 hours; propranolol could be used but to my knowledge no "rescue" med has been required to date.
  - i. Tremor - this typically lasts 1-3 hours so should not require anything besides reassurance; if severe enough, do not allow hot liquids
  - j. Vomiting - this is unusual and time limited; probably too short-lived for anti-emetic medication to help; could try ginger ale or ginger tea
5. Discomfort of repeated needle sticks and other procedures: experienced, trained phlebotomists will obtain blood
  6. Time commitment to completing forms, and attending evaluation, treatment, and follow-up sessions - we will do everything we can to limit time spent; e.g., if patients must wait for their doctor, they will be instructed to complete their self-report forms

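### No vital signs are scheduled between the psilocybin dose and departure at least eight hours later, so a short asymptomatic rise in blood pressure or heart rate could go unrecorded

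*Combined protocol and SAP*

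**What the plan says.** Study Procedures, Visit 3, sets the dosing-day measurements: "Vital signs are taken prior to their dose of psilocybin and prior to leaving the clinic". After the 25 mg dose, patients "spend the next eight hours (longer if needed) with the two therapists". The Lay Summary describes therapist support as "including 8-9 hours accompanying the patient on the day of medication administration". The Schedule of Study Procedures has a single vital-signs mark for Visit 3 and gives no times within the day. Further marks stand at screening, Day -1 and Day +1.

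The Risks/Discomforts/Inconveniences section lists "increased blood pressure" and a rapid heartbeat among the known medical effects. The procedures for minimizing risks then give their size and length. Item 4f on blood pressure reads "systolic pressure may get to 160 mm Hg); as blood pressure rises typically last 1-3 hours", and item 4h on heart rate reads "watchful waiting as to date, fast heart rate has lasted 1-3 hours". Item 4f also favours observation, with a short-acting drug as an option. Neither item gives a measurement interval or a treatment threshold.

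Several safeguards are written in:

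- Exclusion criterion 12 is "Presence of significant or unstable medical illness".
- Item 4a says "a staff member will remain with patient at all times ready to prevent falls as needed".
- A physician can be called for physical reactions, and raised blood pressure is the example given.
- The Rescue Medications list provides a beta-blocker for symptomatic blood pressure elevation.
- Adverse events are collected on the dosing day and reported to the funder.

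**The concern.** The plan expects a transient cardiovascular effect but schedules its readings at times that may fall on either side of it. One is taken before the drug is given. The other is taken at least eight hours later, when by the plan's own figures a rise of typical length may already have ended. An asymptomatic rise gives staff no cue, so it would enter the data only through a reading the protocol does not ask for.

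Hypothesis 1 under Specific Aims is that psilocybin will be acceptable, safe and well tolerated in patients with body dysmorphic disorder. The scheduled data cannot describe the peak blood pressure or heart-rate response to 25 mg. The reassurance in item 4f that pressures have not become dangerous rests on earlier experience, and this trial's scheduled readings could not confirm or contradict it in this population. If the report says that no cardiovascular problem was seen, part of the reason may be when the readings were timed.

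**Working it through.** The plan states no figure to reproduce, and no power or error-rate calculation applies. The check is one of timing.

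**Inputs**

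- Scheduled dosing-day readings: one before the dose and one before leaving (Study Procedures, Visit 3).
- Departure time after the dose, *T*: at least 8 h (Visit 3). 9 h is used as an upper illustration, from the Lay Summary's 8-9 hours.
- Duration of a rise, *d*: 1-3 h for blood pressure (item 4f, called typical rather than a maximum) and 1-3 h for heart rate (item 4h).
- Onset of a rise after the dose, *s*: not given.

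**Formula.** A rise is over before the departure reading when *s* + *d* < *T*, that is, when *s* < *T* − *d*.

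| Duration *d* | Departure at 8 h: over if it starts before | Departure at 9 h: over if it starts before |
|---|---|---|
| 3 h | 8 − 3 = hour 5 | 9 − 3 = hour 6 |
| 2 h | 8 − 2 = hour 6 | 9 − 2 = hour 7 |
| 1 h | 8 − 1 = hour 7 | 9 − 1 = hour 8 |

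The table takes the second reading to be made at departure. If it is made an hour earlier, each cut-off moves an hour earlier.

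**Onset as an assumption.** If a rise began between 0.5 h and 4 h after the dose, it would end between 0.5 + 1 = 1.5 h and 4 + 3 = 7 h, always before an 8 h reading. That range is illustrative and is not in the documents. The nearest information is in Psilocybin Background, which puts the drug's effects at 4-6 hours, but that describes the altered state and not blood pressure. With an 8 h departure, a rise would reach the second reading only if it started late (hour 5 or after for a 3 h rise, hour 7 or after for a 1 h rise) or lasted longer than is typical.

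**Other routes by which a rise could be recorded**

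- *Rescue medication:* the blood pressure entry is tied to symptoms.
- *Physician on call:* this depends on the therapist becoming concerned. An asymptomatic blood pressure rise has to be measured before it can cause concern.
- *Continuous staff presence:* item 4a gives its purpose as preventing falls.
- *Adverse-event recording:* this captures what is noticed or reported. The list of adverse events of special interest includes neither hypertension nor tachycardia.
- *Day +1 assessment:* vital signs and an ECG are scheduled, but on the day after the dose.

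None of these is a scheduled measurement during the session.

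**The case against.** The strongest reply is that in-session readings are implied. The protocol expects a therapist to call a physician about raised blood pressure and mentions drugs to lower it, and neither makes sense without a cuff. Visit 3 does not say that vital signs are taken only twice. The document is a summary form that asks for a concise narrative, its schedule table does not list times within a day, and the Lay Summary says procedures follow earlier depression studies, whose details are not shown. This is fair as inference, and some readings may well have been taken. But no frequency is written down, and where the plan does name times it names two. The point therefore allows for unscheduled readings and does not claim that none were made.

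A second reply is that the choice was reasoned: patients with significant or unstable illness are excluded, staff are present throughout, past rises were short, and measuring interrupts the session. These facts lower the risk to the patient. They do not supply the missing measurement.

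A third is that little depends on it. There is no cardiovascular endpoint, the SAP has no vital-sign analysis, and peak values in 12 open-label patients without a control would only be descriptive. The trial is also finished: all 12 completed and no serious adverse events are reported. All of that stands, and it limits the point to what can be said about safety. Analysis was still under way at the continuation report, so the reporting can still be put right.

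**Conclusion.** The concern holds. The protocol schedules no vital signs in a gap of at least 8 hours after a drug whose blood pressure and heart-rate effects it expects to last 1-3 hours. For an 8 h departure, such a rise is over before the second reading if it starts before hour 5 (3 h rise), hour 6 (2 h) or hour 7 (1 h).

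The conclusion rests on three things: the two readings named for Visit 3 are the only scheduled ones, the second is taken at about departure, and the stated durations apply to these patients. It assumes no onset time. Because the documents give neither the onset nor the frequency of asymptomatic rises, no number of missed participants can be claimed and no harm is alleged.

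No planned test or estimate is affected. Adverse events and the pre-dose, departure and Day +1 assessments still inform Hypothesis 1, but they do not measure the peak effect. This is a worthwhile, low-cost improvement, not a flaw that undermines the trial.

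**What to change.** **For the 12 completed participants.** Report any blood pressure and heart-rate readings taken while the drug was active, with their times. If there are none, state that peak values were not systematically measured, and limit the cardiovascular safety conclusion to adverse events and the pre-dose, departure and Day +1 assessments. The cost is one table or one sentence.

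**For any later use of the protocol.** Add a few timed blood pressure and heart-rate readings in the first hours after the dose to the Visit 3 text and the schedule table, with exact times for the investigators to choose. Report each participant's maximum and the change from the pre-dose value. The cost is a few cuff readings in a unit already staffed for eight hours. The drawback is brief interruption of the session.

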### Psychological Approaches to Anxiety

- During Visit 2 and prior to ingestion of psilocybin during Visit 3, explain anxiety, even fear, may occur
- During Visit 2, train patient in relaxation and breathing techniques that may alleviate anxiety
- On Visit 3, shortly after psilocybin ingestion, remind subject of possible anxiety reaction and that therapist will walk them through it should it occur
- During Visit 3, if patient reports excessive anxiety or fear, walk them through relaxation and breathing techniques taught during Visit 2
- Encourage exploration of psilocybin experience
- Call M.D. if fear is not alleviated by the above

### Rescue Medications

- Anxiety: Lorazepam or alprazolam
- Psychosis: Risperidone
- Headache: Acetaminophen
- Symptomatic elevation in BP: Beta-blocker (e.g., propranolol)
- Nausea/vomiting: Ice chips

### Hospitalization if needed

- Given prior experience with psilocybin treatment, the need for inpatient hospitalization appears unlikely
- In the event that patients require hospitalization they may be admitted to NYSPI 5-South unit.
- Prior to psilocybin dosing [name] will be contacted (email or text [contact]) to ascertain whether backup 5S inpatient bed at NYSPI will be available. In event of lack of availability for such a bed on 5S after it has been offered (e.g., unanticipated issue on inpatient unit) the NYPH. Emergency Room will serve as backup.

**4. Visit 4 (Post-Psilocybin Day 1).** The patient returns to the anxiety clinic and reports any experiences since leaving the clinic as well as having blood, urine, and EKG tests. MRI eligible patients will have another resting state fMRI session, The inverted face task will be repeated.

**5. Visits 5-8 (Post-Psilocybin Weeks 1-3 and 12).** The patient returns 1, 2, 3 and 12 one week later for standard evaluation of psychiatric symptoms, functioning and AE's. These visits may be conducted by phone or secure video.

**6. Telephone visits (Weeks 6 & 9).** The patient is contacted by telephone 6- and 9-weeks post-psilocybin for standard evaluation of psychiatric symptoms and AE's.

**7. Early Withdrawal Visit.** Should the patient or study doctor decide to end the study visits prior to Week 12, if the patient agrees, all Visit 10 (Week 12) ratings including Independent Evaluation will be made.

